8.5 Stopping Rules

Autoimmune epilepsy in the presence of anti VGKC antibodies has not been proved to respond better to IVIG than to no treatment at all. There has not been an open label or a phase 3 trial regarding treatment and outcome, and there are no guidelines or recommendations regarding treatment. There is only level III evidence to support treatment in these patients. Moreover, some patients spontaneously recover back to baseline. Since not easy to diagnose (because of the presenting symptoms often being non convulsive), many times treatment is started months after symptoms start and still prognosis is

good. Therefore we feel comfortable to delay treatment for 5 weeks in the placebo group. We did however decide on stopping rules to prevent any serious implications of delaying treatment.

All participants shall have contact information for the study coordinator. Any adverse event should be reported to the coordinator within 24-48 hours by the patient. The principle investigator will be informed and take the proper steps to ensure patient safety.

1. Severe allergic reaction that call for hospitalization.
2. Any thrombotic event
3. Status epilepticus
4. Increased seizure frequency (more than 50% compared to base line).

8.6 Medical Monitoring

It is the responsibility of the Principal Investigator to oversee the safety of the study at his/her site. This safety monitoring will include careful assessment and appropriate reporting of adverse events as noted above, as well as the construction and implementation of a site data and safety-monitoring plan (see section 10 “Study Monitoring, Auditing, and Inspecting”). Medical monitoring will include a regular assessment of the number and type of serious adverse events.

8.6.1 Internal Data and Safety Monitoring Plan

1. Subject Safety

All subjects enrolled into this study will undergo safety assessments (vital signs, weight, safety blood tests, and cardiac status) at various time points throughout the study. Any abnormal finding will be reported to the PI immediately upon receiving the results.

Subjects will receive phone calls the week after their infusions in which study seizure diaries will be reviewed at all visits for adverse events and any addition or stoppage of new or current medications. This information will be documented in the subject’s study binder. Any information that is collected and is considered abnormal will also be reported to the PI as soon as possible.

All participants shall have contact information for the study coordinator. Any serious adverse event should be reported to the coordinator within 24-48 hours by the patient. The principle investigator will be informed and take the proper steps to ensure patient safety (reporting to the IRB per institutional guidelines and reporting to the sponsor).

1. Severe allergic reaction that call for hospitalization.
2. Any thrombotic event
3. Status epilepticus
4. Increased seizure frequency (more than 50% compared to base line)

In the event PI is not available, the Co-Investigator will be notified of any abnormal findings.

2. Data Integrity

Study inclusion and exclusion will be reviewed with each potential subject to ensure appropriateness for enrollment into the study. Study documents will be completed at the time of the visit and will be entered into the EDC (electronic data capture) system. All data queries will be adjudicated in a timely manner to ensure transcription of data is accurate and complete. The study monitor will have access to the study files and visits to the laboratory and pharmacy will be pre-arranged for the monitor. The PI/Co-I and study team will be available during the monitoring visits.

3. Subject Privacy

Subjects will be seen on Mayo-8 in a clinical exam room. All subjects will have the study explained to them in detail by a qualified member of the study team. The signing of the consent will not occur until all subjects and/or other family members have had ample time to review the consent form and have all their questions answered by the study team.

4. Data Confidentiality

Study binders will be kept in a secure area that is limited to authorized study personnel and admittance to this area is by cardkey access only. Study data will be entered into the EDC (electronic data capture) system. Study data will be identified by a study id and subject initials. A master screening/enrollment log of all subjects screened/enrolled with identifiers will be kept electronically and separate from the study regulatory binder until the study is completed. This will be kept on a secure Mayo server and can only be accessed by Mayo study personnel.

5. Product Accountability

The study drug that is being supplied by the sponsor will be stored and dispensed by the Mayo Research Pharmacy to the study staff. The Mayo Research Pharmacy will maintain all the necessary drug accountability logs such as receipt of drug, dispensation of drug, and temp logs. The monitor will have access to view at any monitoring visit. It is the study staff's responsibility to instruct the subject on the study medication, dose of medication, route of administration, possible side effects, and who to contact in the event of side effects or questions. This will be documented in the study binder as well as the subject's EMR.

6. Study Documentation

All requires study reports will be submitted in a timely manner either to the sponsor and/or the IRB. The regulatory binder will be kept up to date and will be stored in a secure area (same area as study binders). Only authorized study staff, monitors, or other required personnel will have access to the regulatory binder.

7. Study Coordination

A roles and responsibility log will be maintained for the study. A training log that documents the staff training will also be maintained. The staff will receive protocol specific training during the Investigator's meeting as well as complete any sponsor required on-line training. Study staff will ensure that all Mayo required training is completed as it pertains to the study (protection of human subjects). Only those study team members who have completed the appropriate training will perform study specific tests and procedures.

9 Data Handling and Record Keeping

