3.5 Primary Safety Endpoints

- IVIG is a well-known drug and is used routinely in medical practice. We will however as a part of the primary endpoints evaluate the safety and tolerability of IVIG in VGKC Ab associated autoimmune epilepsy.

4 Subject Selection Enrollment and Withdrawal

Target accrual: 30 participants

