6.1 Visit 1 (Screening)

The following will occur at this visit and last up to 4 hours

- Review of medical history
- Review of past and current medication history
- Vital signs (blood pressure, temperature, heart rate, breathing rates, height and weight)
- Neurologic examination
- Undergo memory and cognitive function assessments (RBANS/ KOKMEN Neuropsych testing)
- Review seizure diary
- Confirmation of stable dose of antiepileptic medications

After the assessments are complete and if the subject still meets all study inclusion criteria blood will be drawn for testing. The amount of blood drawn will be approximately 6 tablespoons or 90mL.

This blood test will look at the following:

- kidney and liver function
- Blood sugar and electrolytes

- IgA immunoglobulins
- Antibody testing
- A pregnancy test if you are a female and able to become pregnant
- Blood for repository for future testing

6.2 Visit 2 & 3; Week-1 Day 1 and Day 2

Mayo Clinic Infusions

Within a few days after the subjects initial evaluation they will receive the first two infusions at the Mayo Clinic Infusion Center. The first infusion (0.5g/kg) drug or placebo will be followed by the second infusion (1g/kg) being given the very next day.

The IVIG infusion is given over approximately 6-8 hours depending on the dose and rate of the infusion. Prior to the infusion the subject will have an intravenous catheter (IV) placed in the subjects arm which will be removed after each infusion is completed.

The subject will be given IV fluids (500 mls of normal saline) before and after the infusion of 1g/kg. The subject will be given acetaminophen (Tylenol) (to prevent headache) and Benadryl (to prevent allergic reaction) before all infusions. Before, during and after the infusions, the subject's vital signs will be monitored.

6.3 Visit 4 & 6; Weeks 2 & 4

Phone Calls

The subject will receive a phone call from the study coordinator at week-2 and again at week-4. During these phone calls, the study coordinator will review the subjects seizure history, medications changes (started any new or stopped any medication), or had any adverse events (side effects, illness, and/or hospitalizations).

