6.4 Visit 5 & Visit 7; Week-3 and Week-5

Mayo Clinic Infusion Center

Week-3 infusion (0.6g/kg drug or placebo) will be given 2 weeks following the 2nd infusion. Week-5 (0.6g/kg drug or placebo) infusion will be given 2 weeks after the 3rd infusion (total of 5 weeks).

6.5 Visit 8; Week 6

Mayo Clinic Examination and Unblinding.

During this visit, patients will be seen in clinic. All required assessments will be documented and signed.

- Review current medication history
- Vital signs (blood pressure, temperature, heart rate, breathing rates, and weight)
- Neurological Examination
- Undergo memory and cognitive function assessments (RBANS/KOKMEN- Neuropsych testing)
- Blood draw to check antibody levels.
- Review Seizure Diary

Then, the study physician and the subject will be unblinded.

If the study subject received placebo, they will be given IVIG in an open label fashion through Option Care Home Infusion service using the same dose and schedule as used for the first portion of this study. The last 4 IVIG infusions for those 15 patients, who received placebo for the first 4 treatments, will be given at the patient's home or clinic near their home. These infusions will be given per Option Care's standard operating procedure. In this study we are going to utilize the home care network of Option Care nationwide. Therefore one of the inclusion criteria is that the home treatment network is available where the patient lives.

If the study subject received IVIG, this will be their Research clinic visit, and they will NOT receive any more infusions for the study, they will only receive the phone calls for long term follow up and proceed to VISIT 16, 26 of the tertiary aim.

6.6 Visit 9 & 10; Week 7: Day 1/Day 2

Option Care Home Infusion

Within a 7-10 days after the subjects Week6 evaluation they will receive the first two infusions through Option Care. The first infusion (0.5mg/kg) IVIG will be followed by the second infusion (1g/kg) being given the very next day.

The IVIG infusion is given over approximately 6-8 hours depending on the dose and rate of the infusion. Prior to the infusion the subject will have an intravenous catheter (IV) placed in the subjects arm which will be removed after each infusion is completed.

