6.14 Primary Aim Study Procedures Schedule

Primary Aim	Visit 1	Visit 2	Visit 3	Visit 4	Visit 5	Visit 6	Visit 7
Procedures	Baseline Visit Randomize 1:1 to IVIG or Placebo (all)	Week-1 Day 1 Mayo Infusion Center	Week-1 Day 2 Mayo Infusion Center	Week 2	Week 3 Mayo Infusion Center	Week 4	Week 5 Mayo Infusion Center
Inclusion/Exclusion Criteria Review	B						
Informed Consent	B						
Medial History	B						
Medication Review	B	B	B	B	B	B	B
Seizure History	B						
Safety Labs (Renal, Hepatic, Chem, IgA)	B						
Antibody Testing (VGKC, LGI1, CASPR2)	B						
Neuropsych Testing (RBANS/KOKMEN/TICS)	B						
Vital Signs (B/P, Temp, Height/Weight)	B	B	B		B		B
Infusion Therapy		B	B		B		B
Study Visit (Clinic)	B						
Seizure Diary/Adverse Events	B	B	B	B	B	B	B
Phone Call				B		B	

B=Both IVIG and Placebo groups

I=IVIG group only

P=Placebo at baseline group

SOC=standard of care

P* only in case of abnormal results at baseline as determined by treating physician.

All visits for the Primary Aim have a +/- 3 day window.

All visits for the Tertiary Aim have a +/- 7 day window.

Primary Aim	Crossover Visit 8	Visit 9	Visit 10	Visit 11	Visit 12	Visit 13	Visit 14	Visit 15
Procedures	Week 6 EOS for IVIG Group Start SOC	Week-7 Day 1 Option care home infusion	Week-7 Day 2 Option care home infusion	Week 8	Week 9 Option care home infusion	Week 10	Week 11 Option care home infusion	Week 12 end of Study Visit Placebo Group-Start SOC
Inclusion/Exclusion Criteria Review								
Informed Consent								
Medial History								
Medication Review	B	P	P	P	P	P	P	P
Seizure History	B							P
Safety Labs (Renal, Hepatic, Chem, IgA)	p*							
Antibody Testing (VGKC, LGI1, CASPR2)	I							P
Neuro psych Testing (RBANS/KOKMEN/TICS)	B							P
Vital Signs (B/P, Temp, Height/Weight)	B	P	P		P		P	P
Infusion Therapy		P	P		P		P	
Study Visit (Clinic)	B							P
Seizure Diary/Adverse Events	B	P	P	P	P	P	P	P
Phone Call		P	P	P	P	P	P	

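### Section 8.6.1 commits to safety blood tests and cardiac status over time in all subjects, but the visible schedule plans no safety panel after any IVIG dose and no cardiac assessment beyond vital signs

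*Combined protocol and SAP*

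**What the plan says.** Section 2 lists safety and tolerability of IVIG under the primary aim. Section 3.5 says the study will "as a part of the primary endpoints evaluate the safety and tolerability of IVIG in VGKC Ab associated autoimmune epilepsy". The primary endpoint list in 7.2 contains change in seizure frequency only.

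Section 8.6.1 states that all enrolled subjects undergo "safety assessments (vital signs, weight, safety blood tests, and cardiac status) at various time points throughout the study", and that abnormal findings go to the principal investigator.

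The schedule in 6.14 has a row that begins "Safety Labs (Renal, Hepatic, Chem, IgA". It has two entries: both groups at Visit 1, and p* at Visit 8 (week 6). The legend gives "P=Placebo at baseline group" and "P* only in case of abnormal results at baseline as determined by treating physician". All other cells in the row are blank, and the follow-up schedule in 6.15 has no such row.

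The screening text (6.1) includes "kidney and liver function", with glucose, electrolytes and IgA. For week 6 (6.5), week 12 (6.9), the 6- and 12-month visits (6.11, 6.12) and early termination (6.13), the only blood test listed is "Blood draw to check antibody levels".

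The nearest item to a cardiac assessment is the row "Vital Signs (B/P, Temp, Height/Weight"; the visit text adds heart rate.

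**The concern.** A panel taken once before treatment serves eligibility. It cannot show change on treatment. If 8.6.1 describes what the safety endpoint is built on, the schedule does not collect it.

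Three features of the design make this matter:

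- Week 6 is the only point at which the randomised arms can be compared. Under 6.5 the assessments are done, the physician and subject are then unblinded, and placebo patients go on to open-label IVIG. A placebo panel not taken then cannot be recovered later.
- The protocol itself treats these organ systems as relevant. Section 4.2 excludes severe renal or hepatic disease and recent active ischaemic heart disease, and 4.1 admits patients up to age 85.
- Section 8.2 asks for related abnormal laboratory results to be recorded, but the schedule does not routinely generate any after treatment.

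A renal or hepatic change without symptoms would not be routinely looked for. A report that IVIG was safe would lack the laboratory basis that 8.6.1 describes.

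**Working it through.** The plan gives no figure on this point, so the check is a count of schedule entries (6.14, 6.15) set against the visit text (6.1 to 6.13) and the exposure at each time. Arm sizes are 15 and 15 (7.1).

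| Time | Study infusions so far | Panel, IVIG arm | Panel, placebo-first arm | Blood in visit text |
|---|---|---|---|---|
| Visit 1 | none | yes | yes | panel, IgA, antibodies |
| Weeks 1 to 5 | under way | none | none | none listed |
| Week 6 | 4 IVIG or 4 placebo | none | only if baseline abnormal | antibodies |
| Weeks 7 to 11 | open-label IVIG under way in placebo-first arm | none | none | none listed |
| Week 12 (placebo-first arm) | 4 placebo, then 4 IVIG | no visit | none | antibodies |
| 6- and 12-month visits | all complete | none | none | antibodies |
| Early termination | varies | none | none | antibodies |

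**Post-IVIG panels.** IVIG arm: 0 of 15. Placebo-first arm: 0 of 15. Total: 0 of 30.

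**The conditional week-6 entry.** By the legend it applies to the placebo-first group only. Under 6.6 these patients receive their first IVIG 7 to 10 days after the week-6 evaluation, so any value obtained is a pre-IVIG value. The IVIG arm has no week-6 panel to set beside it. The entry therefore supplies neither a post-IVIG result nor a between-arm comparison.

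**Cardiac status.** Section 8.6.1 lists it separately from vital signs. No row in 6.14 or 6.15 and no item in 6.1 to 6.13 names a cardiac assessment, so the count is 0 beyond blood pressure and heart rate.

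**Week-6 blood in the placebo arm.** The antibody row in 6.14 is coded for the IVIG group only at week 6. Section 6.5 lists the draw without restricting it to one arm. Sections 3.2 and 7.2 describe draws at baseline and 6 weeks, with 12 weeks for the placebo group only. The schedule and the text disagree.

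**Size of the remedy.** Week 6 in both arms: 15 + 15 = 30 panels. Week 12 in the placebo-first arm: 15. Total: 30 + 15 = 45, plus any at early termination. If the 6.14 antibody code is followed, up to 15 placebo patients would need a week-6 draw that the schedule does not otherwise give them.

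**The case against.** Several points on the other side are fair.

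- **Labs are not simply taken once.** The conditional week-6 repeat exists, and a flat claim of a single draw would be wrong. It does not fill the gap, because it covers only patients who have not yet had IVIG.
- **Laboratory values after IVIG may still arise.** Section 8.2 requires adverse events to be sought at every contact, with examination where appropriate, so events may prompt tests, and antibody levels are drawn. A reader might infer that no laboratory information could exist in exposed patients, or that safety cannot be assessed at all. The documents do not support that; the gap is in planned safety panels.
- **Cardiovascular observation is not absent.** Vital signs are taken at clinic visits, and before, during and after the week-1 and week-7 infusions. What is missing is any definition or scheduling of the separate item that 8.6.1 names.
- **Two appendices cannot be seen.** Section 3.2 refers to infusion procedures of the clinic and the home-infusion agency in appendices 1 and 2. Either could contain checks, so the counts apply to the visible schedule and visit text.
- **Endpoint status is mixed.** Section 7.2 omits safety, and 3.5 promises no specific laboratory endpoint. That is a further inconsistency to settle. It does not remove the commitment in 8.6.1.
- **A comparison of 15 with 15 is weak.** With 0 events in 15 the two-sided 95% exact upper limit is 1 − 0.025^(1/15) = 21.8%. This limits what the panels could establish and argues for a descriptive summary, but 8.6.1 still says that the tests are done in all subjects.

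**Conclusion.** The contradiction stands. Section 8.6.1 describes repeated safety blood tests and cardiac status in all subjects. The visible schedule gives one panel to everyone before treatment, a conditional pre-IVIG repeat in part of one arm, no panel after IVIG in any of 30 patients, and no cardiac item beyond vital signs. Planned laboratory safety of IVIG cannot be compared between arms, and the safety endpoint rests on adverse events, vital signs and event-driven tests.

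This assumes that p* means what the legend says and that the unseen appendices add no laboratory or cardiac checks. It does not show that IVIG is unsafe or that safety goes unmonitored. A reader might also infer that the remedy needs no extra blood draw. That holds if 6.5 governs week 6, but not if the 6.14 code does.

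**What to change.** 1. Reconcile 8.6.1, 3.5 and 7.2 with 6.5, 6.9, 6.13 and 6.14, and state whether safety is a primary endpoint.
2. To deliver what 8.6.1 states, run the baseline renal, hepatic and chemistry panel as a safety outcome at week 6 (both arms), week 12 (placebo-first arm) and early termination. Recode the Safety Labs row to match. Summarise change from baseline by arm, with week 6 as the randomised comparison. Otherwise remove the commitment from 8.6.1 and limit the safety conclusion to what is measured.
3. Define cardiac status and give it a schedule row, or delete it from 8.6.1.
4. Reconcile the week-6 antibody draw between 6.14 and sections 3.2, 6.5 and 7.2.

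Cost: a text and schedule amendment, about 45 routine panels plus any at early termination, and no extra visit. If 6.5 governs, the panels use blood draws already planned; if the 6.14 code governs, up to 15 placebo patients need a week-6 draw. Choosing to withdraw the commitment costs only the text amendment and a narrower safety claim.

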9.1 Confidentiality

Information about study subjects will be kept confidential and managed according to the requirements of the Health Insurance Portability and Accountability Act of 1996 (HIPAA). Those regulations require a signed subject authorization informing the subject of the following:

- What protected health information (PHI) will be collected from subjects in this study
- Who will have access to that information and why
- Who will use or disclose that information
- The rights of a research subject to revoke their authorization for use of their PHI.

In the event that a subject revokes authorization to collect or use PHI, the investigator, by regulation, retains the ability to use all information collected prior to the revocation of subject authorization. For subjects that have revoked authorization to collect or use PHI, attempts should be made to obtain permission to collect at least vital status (long term survival status that the subject is alive) at the end of their scheduled study period.

9.2 Source Documents

Source data is all information, original records of clinical findings, observations, or other activities in a clinical trial necessary for the reconstruction and evaluation of the trial. Source data are contained in source documents. Examples of these original documents, and data records include: hospital records, clinical and office charts, laboratory notes, memoranda, subjects' diaries or evaluation checklists, pharmacy dispensing records, recorded data from automated instruments, copies or transcriptions certified after verification as being accurate and complete, microfiches, photographic negatives, microfilm or magnetic media, x-rays, subject files, and records kept at the pharmacy, at the laboratories, and at medico-technical departments involved in the clinical trial.

9.3 Case Report Forms

The study case report form (CRF) is the primary data collection instrument for the study. All data requested on the CRF must be recorded. All missing data must be explained. If a space on the CRF is left blank because the procedure was not done or the question was not asked, write "N/D". If the item is not applicable to the individual case, write "N/A". All entries should be printed legibly in black ink. If any entry error has been made, to correct such an error, draw a single straight line through the incorrect entry and enter the correct data above it. All such changes must be initialed and dated. Do not erase or use "white-out" for errors. For clarification of illegible or uncertain entries, print the clarification above the item, then initial and date it. If the reason for the correction is not clear or needs additional explanation, neatly include the details to justify the correction.

